8.3.3 Missing Post-baseline Evaluation in Open-label Treatment Period

For the descriptive summary of mean monthly value calculated using the monthly value from each of months 11, 12, and 13 (week 41 through 52) of the DBTP, if a subject has at least one monthly value at months 11, 12, and 13 (week 13 through 24), then the subject contributes to the summary statistics.

8.4 Detection of Bias

This study has been designed to minimize potential bias by allocating treatment groups randomly, assessing endpoints and handling withdrawals without knowledge of the treatment. Other factors that may bias the results of the study include:

- important protocol deviations likely to impact the analysis and interpretation of the efficacy endpoints
- inadvertent breaking of the blind before formal unblinding
- investigational product dosing non-compliance
- the timing of and reasons for early withdrawal from treatment and from study

The incidence of these factors may be assessed. Important protocol deviations will be listed and/or tabulated in the clinical study report (CSR). If necessary, the incidence of other factors will be tabulated.

Any breaking of the blind for individual subjects prior to formal unblinding of the study will be documented in the CSR.

The timing of and reasons for early withdrawal from treatment and from study will be tabulated and/or listed.

8.5 Outliers

Histograms will be examined to identify outliers in any of the continuous variables used in the analyses. Unexpected and/or unexplained values in categorical data will be identified by utilizing frequency tables.

Outliers due to data entry errors will be corrected by the study team before final database lock. The validity of any questionable values or outliers will be confirmed.

Outliers or any questionable values with confirmed validity will be included in the analyses. However, ad-hoc sensitivity analyses may be conducted to evaluate the influence of extreme values in the data.

8.6 Distributional Characteristics

Continuous endpoints of change from baseline value will be analyzed under normality assumption. If they deviate appreciably from normality, appropriate transformations or the non-parametric alternatives will be used, such as Quade test ([Quade D, 1966](#)).

8.7 Validation of Statistical Analyses

Programs will be developed, maintained, and output will be verified in accordance with current risk-based quality control procedures.

Tables, figures, and listings will be produced **and validated in accordance with SOP-430399. Standard macros programs will be used when available.**

The production environment for statistical analyses consists of Amgen-supported versions of statistical analysis software; for example, the SAS System version 9.4 or higher.

9. Statistical Methods of Analysis

9.1 General Considerations

Formal statistical analyses using statistical models and hypothesis testing will be performed for the nonopioid-treated cohort only. Descriptive statistics will be produced for the opioid-treated cohort. **The classification of cohorts (opioid-treated and nonopioid-treated) used for the primary analysis will be based on the cohort value determined at randomization. As sensitivity analysis, the primary endpoint, secondary endpoints, and change from baseline in mean monthly opioid/opioid-containing medication days will be summarized descriptively for the 'observed' opioid-treated subjects who reported >4 days of opioid medication use in the eDiary data during the last 28 days of baseline period.**

Summary statistics will be computed by treatment group and visit. For continuous endpoints, the following descriptive statistics will be computed: number of observations, means, medians, standard deviations, standard errors, first and third quartiles, minimums and maximums, and 2-sided 95% CIs of the means (CIs will be provided for efficacy endpoints only). For categorical endpoints, the summaries will contain the number and percentage of subjects in each category.

The dichotomous efficacy endpoints will be analyzed using the stratified Cochran-Mantel-Haenszel (CMH) test after the missing data is imputed as nonresponse. Continuous secondary endpoints will be analyzed using a linear mixed effects model including treatment group, baseline value, stratification factor, scheduled visit, and the interaction of treatment group with scheduled visit, without any imputation for missing data at the monthly level. **In case more than 10% subjects had stratification error within non-opioid treated cohort (ie. stratified incorrectly between the with vs. without concomitant oral migraine preventive medication strata), sensitivity analysis will be conducted for the model-based analysis for primary and secondary endpoints, using the ‘observed’ concomitant oral migraine preventive medication reported by site as strata in CMH tests.**

The 2 erenumab dose groups will be compared with placebo for the primary and secondary efficacy endpoints in the nonopioid-treated cohort using a simple fixed sequence procedure with study-wise type I error rate $\alpha = 0.05$. The order of the endpoints to be tested is prespecified below. If any test is not significant at the $\alpha = 0.05$ level, then no further testing will be performed.

Primary and secondary endpoints in erenumab 140 mg versus placebo:

1. Absence of MOH at month 6 of DBTP (140 mg)
2. Change from baseline in mean monthly AHMD over months 4, 5, and 6 (**week 13 through 24**) of the DBTP (140 mg)
3. Sustained MOH remission during DBTP (140 mg)

Primary and secondary endpoints in erenumab 70 mg versus placebo:

4. Absence of MOH at month 6 of the DBTP (70 mg)
5. Change from baseline in mean monthly AHMD over months 4, 5, and 6 (**week 13 through 24**) of the DBTP (70 mg)
6. Sustained MOH remission during DBTP (70 mg)

Patient reported outcome-related secondary endpoints for the non-EU region (**United States, Australia**):

7. Change from the baseline in mean monthly average physical impairment domain scores as measured by the MPFID over months 4, 5, and 6 of the DBTP (140 mg)
8. Change from the baseline in mean monthly average impact on everyday activities domain scores as measured by the MPFID over months 4, 5, and 6 of the DBTP (140 mg)
9. Change from the baseline in mean monthly average physical impairment domain scores as measured by the MPFID over months 4, 5, and 6 of the DBTP (70 mg)

10. Change from the baseline in mean monthly average impact on everyday activities domain scores as measured by the MPFID over months 4, 5, and 6 of the DBTP (70 mg)

OR

Patient reported outcome-related secondary endpoints for the EU region (**including United Kingdom**):

11. Change from baseline in mean HIT-6 score over months 4, 5, and 6 (**week 13 through 24**) of the DBTP (140 mg)

12. Change from baseline in mean HIT-6 score over months 4, 5, and 6 (**week 13 through 24**) of the DBTP (70 mg)

Analysis for efficacy endpoints during the OLTP will be summarized separately for nonopioid-treated and opioid-treated cohorts.

9.2 Subject Accountability

For the primary analysis at week-24 the disposition of all enrolled subjects will be tabulated by the randomized treatment group. The summary will include the number of subjects who are randomized, the number and percent of subjects who receive the double-blind IP, who complete double-blind IP, discontinue double-blind IP and reasons for discontinuing, who complete the 24-week DBTP, and who withdraw prematurely from the study before completion of the 24-week DBTP and their reasons for withdrawal.

Summary of subjects who discontinue investigational product/study due to COVID-19 control measures will be included.

For the **primary and** final analysis, disposition of the OLTP and the entire study will be tabulated, which includes the number and percent of subjects who enter the OLTP, who receive the open-label erenumab who complete open-label erenumab, discontinue erenumab and reasons for discontinuing, who complete the study, and who withdraw prematurely from the study and their reasons for withdrawal. **Summary of subjects who discontinue investigational product/study due to COVID-19 control measures will be included.**

9.3 Important Protocol Deviations

Important Protocol Deviations (IPDs) categories are defined by the study team before the first subject's initial visit and updated during the IPD reviews throughout the study prior to database lock. These definitions of IPD categories, subcategory codes, and descriptions will be used during the course of the study. Eligibility deviations are defined in the protocol. IPDs will be summarized by randomized treatment group. **Protocol**

Deviations (PDs) related to COVID-19 control measures will be summarized separately.

9.4 Demographic and Baseline Characteristics

Subject demographic and baseline characteristics will be summarized using descriptive statistics by randomized treatment group and overall study population using FAS. If multiple races have been reported for a subject, the subject will be categorized as multiple races.

At double-blinded baseline, following demographic and baseline characteristics will be summarized:

- Age (years)
- Sex
- Ethnicity
- Race
- Region (North America vs Others)
- Height (cm)
- Weight (kg)
- Body mass index (BMI, kg/m²)
- Targeted neurological disease diagnosis at baseline
- **Prior history of treatment with onabotulinumtoxinA**
- **Prior history of depression**
- Disease duration of migraine with or without aura
- **Disease duration of chronic migraine with or without aura**
- Age at onset of migraine
- Age at onset of chronic migraine
- **Prior migraine preventive treatment and reasons for discontinuation by medication category**
- **Concomitant oral migraine preventive treatment by medication category**
- **Number of prior migraine preventive treatment failures by medication category**
- Acute headache medication used during baseline period:
 - a) Migraine-specific
 - b) Non-migraine-specific
- Monthly migraine days during baseline period
- **Monthly migraine-free days during baseline period**
- Monthly headache days during baseline period

- Monthly **headache** days with **at least** moderate pain intensity during baseline period
- Monthly acute migraine-specific medication days during baseline period
- Monthly acute migraine-specific medication days during baseline period among baseline users
- Monthly acute headache medication days during baseline period
- **Monthly opioid/opioid-containing medication days (opioid-treated cohort only)**
- **Overuse of acute headache medication during the baseline period**
- Overuse of triptan during the baseline period
- Overuse of simple analgesics/NSAIDs during the baseline period
- Overuse of combination analgesics during the baseline period
- Overuse of combination therapies during the baseline period
- Monthly average **headache** pain intensity during baseline period
- **Monthly average MPFID physical impairment score during baseline period**
- **Monthly average MPFID overall impact on everyday activities score during baseline period**
- Beck Depression Inventory (BDI)-II total score severity grade
- Headache Impact Test (HIT-6) total score
- MFIQ impact on physical functioning
- MFIQ impact on usual activities
- **MFIQ overall impact on usual activities**
- MFIQ impact on social functioning
- MFIQ impact on emotional functioning
- Allodynia Symptoms as measured by the Allodynia Symptoms Checklist 12-items (ASC-12)
- Migraine Disability Assessment Questionnaire MIDAS) **total score**
- **Migraine Disability Assessment Questionnaire (MIDAS) presenteeism score**
- **Migraine Disability Assessment Questionnaire (MIDAS) total score**
- Generalized Anxiety Disorder 7-Item Scale (GAD-7) score

9.5 Efficacy Analyses

The primary analysis of efficacy endpoints **during the DBTP** will utilize the efficacy analysis set. Subjects will be analyzed according to their randomized treatment group regardless of the actual treatment received during the study.

Table 9-1. Primary Efficacy Endpoint Summary Table

Endpoint	Primary Summary and Analysis Method	Sensitivity Analysis
Absence of MOH at month 6 (week 24) as defined by mean monthly AHMD < 10 days over months 4, 5, and 6 (week 13 through 24) OR mean MHD < 14 days over months 4, 5 and 6 (week 13 through 24) where AHMD include any eDiary day in which an acute headache medication intake is reported.	
 The responder rate of subjects with absence of MOH by treatment group with missing data imputed as non-response imputation (NRI) A stratified CMH test with NRI adjusted by original stratified values Breslow-Day test will be conducted to test the homogeneity of the odds ratios across the original stratification factors 	
 Same as primary analysis method but using observed concomitant oral preventive medication status as the stratification factor. Same as primary analysis method but only include subjects with observed monthly AHMD and MHD in each of the month over month 4, 5 and 6

Table 9-2. Secondary Efficacy Endpoints Summary Table

Endpoint	Primary Summary and Analysis Method	Sensitivity Analysis

 Change from baseline in mean monthly AHMD over months 4, 5, and 6 (week 13 through 24) of the DBTP (Note: Result at each timepoint during DBTP will also be generated in the same model.) 	
 Summary statistics by visit using observed data and 95% CI of mean change from baseline at each visit by treatment group Least squares means by visit using a linear mixed effects repeated measure model adjusted by baseline value, original stratification factor, scheduled visit, and the interaction of treatment group with scheduled visit, without any imputation for missing data at monthly level Treatment difference between each erenumab dose group and placebo) with the 95% CI, and p-value from the model in #2 	Least squares means by visit using a linear mixed effects repeated measure model adjusted by baseline value, observed concomitant oral migraine preventive medication status, scheduled visit, and the interaction of treatment group with scheduled visit, without any imputation for missing data at monthly level

Endpoint	Primary Summary and Analysis Method	Sensitivity Analysis
2. Sustained MOH remission during DBTP, as defined by absence of MOH at months 3 (week 12) and 6 (week 24) of the DBTP, and “absence of MOH” is achieved when mean monthly AHMD < 10 days OR mean MHD < 14 days over the respective 3-month period	Same as primary endpoint	Same as primary analysis method but using observed concomitant oral preventive medication status as stratification factor.
3. Change from baseline in mean monthly average physical impairment domain scores as measured by the MPFID over months 4, 5, and 6 (week 13 through 24) of the DBTP (non-EU region) 4. Change from baseline in mean monthly average impact on everyday activities domain scores as measured by the MPFID over months 4, 5, and 6 (week 13 through 24) of the DBTP (non-EU region) 5. Change from baseline in mean HIT-6 total score over months 4, 5, and 6 (week 13 through 24) of the DBTP (EU region) (Note: Result at each timepoint during DBTP will also be generated in the same model.)	Same as above	Same as above

9.5.1 Analyses of Primary Efficacy Endpoint

The primary comparison of absence of MOH at month 6 between each erenumab group and placebo will be analyzed using a stratified CMH test with nonresponse imputation. The proportion of subjects with absence of MOH will be reported for each treatment group. The odds ratio between each erenumab group and placebo, the corresponding 95% CI and p-value will be reported. **Breslow-Day test will be conducted to test the homogeneity of the odds ratios across the strata.**

As a supportive analysis, the primary efficacy endpoint will also be analyzed including subjects with observed AHMD and MHD data at each month during months 4, 5, and 6 (week 13 through 24).

9.5.2 Analyses of Secondary Efficacy Endpoints

The continuous secondary endpoints will be analyzed using a linear mixed effects repeated measure model will include treatment group, baseline value, stratification factor, scheduled visit, and the interaction of treatment group with scheduled visit, without any imputation for missing data. If applicable, the first-order autoregressive covariance structure is assumed. Least squares means (LSMs) for each treatment group, standard errors, associated 95% confidence intervals, difference of LSMs compared to placebo group, associated 95% confidence intervals and nominal two-sided p-values will be tabulated by visit.

The dichotomized secondary endpoint will be analyzed using the same method as for the primary endpoint in [Section 9.5.1](#).

9.5.3 Analyses of Exploratory Efficacy Endpoints in Double-blind Treatment Period

For exploratory efficacy endpoints during the DBTP, summary statistics and analysis method will be conducted in the same way as that for the primary and secondary efficacy endpoints as described in [Section 9.5.1](#) and in [Section 9.5.2](#). **No sensitivity analysis is planned for exploratory endpoints except the sensitivity analysis for opioid-treated cohort as specified in section 9.1. For continuous endpoints collected only at one or two timepoints post-baseline during the DBTP, analysis of covariance (ANCOVA) adjusting baseline value and stratification factor will be used instead. BDI-II and PGIC will be summarized by category score using observed data. The shift from baseline in severity category score of BDI-II will be analyzed at week 12 and week 24 using observed data.**

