10.4.2.2 Efficacy Analyses

Endpoint	Statistical Analysis Methods
Primary	The primary comparison of absence of MOH at month 6 (week 24) between each erenumab dosing group and placebo will be analyzed using a stratified CMH test after the missing data are imputed as nonresponse. The proportion of subjects with absence of MOH will be reported for each treatment group. The odds ratio between each erenumab group and placebo, the corresponding 95% CI and p-value will be reported.
Secondary	The continuous secondary endpoints will be analyzed using a linear mixed effects repeated measure model including treatment group, baseline value, stratification factor, scheduled visit, and the interaction of treatment group with scheduled visit, without any imputation for missing data. The LSM change from baseline with the 95% CI for each treatment group, the treatment difference (each erenumab group – placebo) with the 95% CI, and p-value will be reported. The dichotomized secondary endpoint will be analyzed using the same methodology as for the primary endpoint.
Exploratory	The continuous exploratory efficacy endpoints at each assessment time will be analyzed using the repeated measures linear mixed effects model that includes treatment group, baseline values, stratification factor, scheduled visit, and the interaction of treatment and scheduled visit without any imputation for missing data. Dichotomized endpoints will be analyzed using a stratified CMH test with missing data imputed as nonresponse. The difference in LSM (or odds ratios) of treatment groups and placebo with associated 95% CIs and p-values will be reported.

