		
and missing endpoints evaluations at postbaseline during OLTP
 
 • Section 8.7 updated to clarify TFLs will be produced and validated in accordance with SOP-430399 • Section 9.1 updated to include descriptive summary of primary, secondary and change from baseline in mean monthly opioid/opioid-containing medication days for the 'observed' opioid-treated cohort as sensitivity analyses • Section 9.2 and 9.3 included summary of protocol deviations related to COVID-19 measures • Section 9.4 updated to include additional summary of baseline characteristics • Table 9-1, Table 9-2, and Section 9.5 updated to include additional sensitivity analyses to examine the derived values of concomitant oral migraine preventive medications with respect to the primary and secondary endpoints • Section 9.5 updated to include breslow-test for the analysis of dichotomized endpoints, ANCOVA for continuous endpoints collected at one or two timepoints postbaseline, and the analysis of BDI-II and PGIC • Section 9.6 updated to include exposure-adjusted subject incidence for the DBTP, serious TEAE occurring on or after the COVID infection, device-related AEs and the EOI COVID-19 SMQ (Narrow) • Section 10 updated to specify the addition of ditans in the list of acute headache medication and changes in definition of efficacy analysis set • Section 12 updated to clarify the scope of this Statistical Analysis Plan will not include the data for biomarker development and optional interview-based substudy • Editorial/changes were made throughout the document to improve overall clarity

Table of Contents

Table of Contents	4
1. Introduction.....	9
2. Objectives, Endpoints and Hypotheses.....	9
2.1 Objectives and Endpoints.....	9
2.2 Hypotheses and/or Estimations.....	16
3. Study Overview	17
3.1 Study Design.....	17
3.2 Sample Size.....	17
3.3 Adaptive Design.....	18
4. Covariates and Subgroups	18
4.1 Planned Covariates.....	18
4.2 Subgroups.....	18
5. Definitions.....	19
5.1 Definition of Terms Included in Study Endpoints	19
5.1.1 Efficacy Endpoints Based on Daily eDiary Collection.....	19
5.1.2 Efficacy Endpoints Based on Monthly Collection	25
5.1.3 Safety Endpoints	27
5.2 Study Dates	28
5.3 Study Points of Reference.....	29
5.4 Study Time Intervals	30
5.4.1 Study Periods.....	30
5.4.2 Monthly Intervals for Efficacy Endpoints Derived From Daily Diary Collection	30
5.4.3 Analysis Visits for Endpoints Based on Monthly Collection	32

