5.4.3 Analysis Visits for Endpoints Based on Monthly Collection

Since the actual visit for a subject may not exactly coincide with their targeted visit date, the actual visit date is mapped to the analysis visit as in [Table 5-2](#) to [Table 5-7](#).

By-visit data collected on or before the first OLTP dose date belong to DBTP. Data collected after the first OLTP dose date, not including the safety follow-up visit, belong to OLTP. Any data occurred after EOS date will not be included in the analysis except antibody data.

For by-visit summaries, if more than one visit with non-missing measurement (including the unscheduled visits, ie, CPEVENT = 'UNSCHED') fall within the same visit window, the following rules will be applied according to the order described below for selecting one visit per visit window for summary:

1. Scheduled visit will be used regardless of the distance from the target day. Unscheduled visit will only be used when there is no measurement from scheduled visit in the visit window.
2. The visit closest to the target day will be considered for analysis.
3. If two assessment dates are equidistant from the target date, the latter visit will be considered for analysis.

Table 5-2. HIT-6 and MFIQ Analysis Visit Windows

Study Period	Analysis Visit	Target Day	Visit Window (Study Day)
Double-blind Treatment Period	Day 1 (Baseline)	1	Last measurement prior or on Day 1
	Week 4 (Month 1)	29	16 to 43
	Week 8 (Month 2)	57	44 to 71
	Week 12 (Month 3)	85	72 to 99
	Week 16 (Month 4)	113	100 to 127
	Week 20 (Month 5)	141	128 to 155
	Week 24 (Month 6)	169	156 to Week 24 dose date, if available, else to 183
Open-label Treatment Period	Week 52 (Month 13)	365	352 to 379

Table 5-3. MIDAS Analysis Visit Windows

Study Period	Analysis Visit	Target Day	Visit Window (Study Day)
Double-blind Treatment Period	Day 1 (Baseline)	1	Last measurement ≤ Day 1
	Week 12 (Month 3)	85	72 to 99
	Week 24 (Month 6)	169	156 to Week 24 dose date, if available, else to 183
Open-label Treatment Period	Week 52 (Month 13)	365	352 to 379

Table 5-4. ASC-12/GAD-7/BDI-II/Sleep Questionnaire Analysis Visit Windows

Study Period	Analysis Visit	Target Day	Visit Window (Study Day)
Double-blind Treatment Period	Day 1 (Baseline)	1	Last measurement ≤ Day 1
	Week 12 (Month 3)	85	72 to 99
	Week 24 (Month 6)	169	156 to Week 24 dose date, if available, else to 183

Table 5-5. PGIC Analysis Visit Windows

Study Period	Analysis Visit	Target Day	Visit Window (Study Day)

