8.3 Handling of Missing and Incomplete Data

Subjects may miss specific data points for a variety of reasons. In general, data could be missing due to a subject's early withdrawal from the study, a missed visit, or inability to evaluate an endpoint at a particular point in time. For this study, efficacy endpoints are clinical outcome assessments (COAs) collected via daily eDiary or monthly assessments at the office visits. Missing COAs with respect to quality-of-life questionnaires (MPFID, HIT-6, MFIQ, MIDAS, Sleep questionnaire, Allodynia symptom checklist, BDI-II, GAD-7 and PGIC) will not be imputed. **Missing items in each eCOA questionnaire will be handled based on the scoring algorithm for each COA.**

Subjects could miss entering several days of data in eDiary within each monthly interval. The calculation of monthly measurements about subjects' migraine and non-migraine headaches will be handled using the following method, also described in [Section 5.1.1](#).

- For each monthly interval with ≥ 14 days of eDiary use:

- Monthly frequency measurements will be prorated to 28-day equivalents. Prorated result does not need to be rounded.
- Monthly average scores will be calculated as the average of observed scores.
- For monthly intervals with < 14 days of eDiary use, all monthly measurements will be set as missing.

Missing safety endpoints will not be imputed **except for partial AE start dates**. Missing or incomplete dates will be listed as reported, except for incomplete start date of an AE or concomitant medication, which will be imputed as follows:

Missing	Imputation	Exception on adverse event start date
Day	01	Default to study day 1 if an adverse event started the same year and month as study day 1 and the flag indicates that the adverse event started on or after the first dose of investigational product on the Events eCRF
Day/Month	01 Jan	Default to study day 1 if an adverse event started the same year as study day 1 and the flag indicates that the adverse event started on or after the first dose of investigational product on the Events eCRF
Day/Month/Year	None	—

Similarly, incomplete dates of HRU will be imputed using the same imputation rule as above.

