8.3.2 Missing Post-baseline Evaluation in Double-blind Treatment Period

Primary analysis of dichotomous efficacy endpoints during the DBTP will be conducted using Cochran-Mantel-Haenszel test (CMH) after the missing data are imputed as nonresponse. Primary analysis of continuous efficacy endpoints during the DBTP will be conducted using the repeated measures linear mixed effects model including observed data without imputation.

For the descriptive summary of mean monthly value calculated using the monthly value from each of months 4, 5, and 6 (**week 13 through 24**) of the DBTP, if a subject has at least one monthly value at months 4, 5, and 6 (**week 13 through 24**), then the subject contributes to the summary statistics.

If the proportion of missing data in primary endpoint is high (eg, > 20% for primary analysis at week 24), further analysis will be performed to

- examine the frequency and reason of missing data
- determine if there are any patterns in the missing data
- distinguish true missing values from other unknown values (eg, due to measurement or sample processing error)

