9.7 Other Analyses

9.7.1 Analyses of Health Economic Endpoints

Health Resource Utilization Questionnaire (HRU)

The questionnaire is designed to collect data on HRU. Specifically, the aim is to capture frequency of **headache**-related hospitalizations and outpatient visits including emergency department visits, urgent care visits, and other clinical visits. The recall period for the HRU questionnaire is 24 weeks, and the HRU questionnaire will be administered on day 1, and week 24 of the DBTP. The questionnaire assessed at the early termination visit before week 24 should only include HRU recalled since the previous assessment at day 1 to avoid collecting duplicate information.

10. Changes From Protocol-specified Analyses

During the development of SAP amendment, it was realized that there are protocol-specified analyses that cannot be implemented/performed and the

protocol is not required to be amended. Ditans is included in the list of acute headache medications in Section 5.1. The definition of efficacy analysis set stated in the protocol is not applicable to all efficacy endpoints and has been corrected in Section 6.2 to what was intended. These changes will also be documented in the clinical study report.

11. Literature Citations / References

Quade, D. (1966), Rank analysis of covariance, University of North Carolina, Institute of Statistics Mimeo Series. No 483.

12. Data Not Covered by This Plan

There are no plans to specifically analyze or summarize the following data points.

- Data for biomarker development
- Data from the optional interview-based substudy

13. Appendices

Not applicable

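### For exploratory outcomes measured at weeks 12 and 24, SAP 9.5.3 swaps the protocol's repeated-measures model for ANCOVA, so week-12 data from subjects missing week 24 go unused in the week-24 comparison

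*SAP*

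**What the plan says.** **Protocol 10.4.2.2** sets the method for exploratory outcomes: "The continuous exploratory efficacy endpoints at each assessment time will be analyzed using the repeated measures linear mixed effects model". Its terms are treatment, baseline, stratification factor, visit and treatment by visit, with no imputation. Treatment differences, confidence intervals and p-values are to be reported.

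**SAP 9.5.3** makes an exception, with ANCOVA to be used in place of that model: "For continuous endpoints collected only at one or two timepoints post-baseline during the DBTP, analysis of covariance (ANCOVA) adjusting baseline value and stratification factor". It lists no visit term. It plans no sensitivity analysis for exploratory endpoints other than one for the opioid-treated cohort.

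**SAP 8.3.2** keeps the protocol's rule with no exception: "Primary analysis of continuous efficacy endpoints during the DBTP will be conducted using the repeated measures linear mixed effects model including observed data without imputation".

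**SAP 8.3** on missing scores: "Missing COAs with respect to quality-of-life questionnaires (MPFID, HIT-6, MFIQ, MIDAS, Sleep questionnaire, Allodynia symptom checklist, BDI-II, GAD-7 and PGIC) will not be imputed".

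**SAP Tables 5-3 and 5-4** give MIDAS, and the scales under "ASC-12/GAD-7/BDI-II/Sleep Questionnaire Analysis Visit Windows", two post-baseline visits in the double-blind period: week 12 (days 72 to 99) and week 24 (from day 156).

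**Where the change is recorded.** The SAP version history lists, as an update to Section 9.5, "ANCOVA for continuous endpoints collected at one or two timepoints postbaseline". Section 10, which is reserved for departures from the protocol, names two others: "Ditans is included in the list of acute headache medications in Section 5.1" and "The definition of efficacy analysis set stated in the protocol is not applicable to all efficacy endpoints". The ANCOVA switch is not there, and no reason for it appears anywhere.

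**The concern.** With two post-baseline visits the protocol's model is fully estimable, so nothing forces the change. The model borrows from week 12 when week 24 is missing, and its week-24 contrast stays valid if missingness depends only on observed values, including the week-12 score. A week-24 ANCOVA uses only subjects seen at week 24. It gives up some precision, and it can be biased if subjects doing badly at week 12 leave more often in one arm than in another.

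The early-termination visit often does not fill the gap. The footnote to Protocol Table 2-1 places it about 28 (+3) days after the last dose. A subject last dosed at week 12 (day 85) is then seen around days 113 to 116, and one last dosed at week 16 (day 113) around days 141 to 144. Days 100 to 155 belong to no analysis window for these scales.

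At stake are the reported week-24 differences in disability, anxiety, allodynia and sleep, and the six-month cumulative MIDAS change. The SAP has no rule for forming that sum when one visit is missing.

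**Working it through.** **1. The plan's own figure.** The documents give no figure for these outcomes. Their sample-size statement (Protocol 10.1, SAP 3.2) is 183 per group, 33.1% vs 50.5%, 20% dropout and 85% power. Treating dropout as lost subjects, n = 183 × 0.8 = 146.4 per arm:

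- pooled SE = √(2 × 0.418 × 0.582 / 146.4) = 0.0577
- unpooled SE = √((0.331 × 0.669 + 0.505 × 0.495) / 146.4) = 0.0567
- z = (0.174 − 1.96 × 0.0577) / 0.0567 = 1.08, so power is 85.9%

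This reproduces the stated 85%. Its only use here is the 20%: about 146 of 183 subjects per arm have week-24 data and 37 do not.

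**2. Precision.** Let n_c subjects in an arm have week 24, and m have week 12 only. Let ρ be the baseline-adjusted week 12 to week 24 correlation. In large samples, with monotone missingness,

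Var(mixed model) / Var(completers) = 1 − ρ² × m / (n_c + m).

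Neither m nor ρ is in the documents. I assume that 25% to 100% of the 37 have week-12 data and that ρ is 0.3 to 0.8. Reduction in week-24 variance with n_c = 146:

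| Share with week 12 | m | ρ = 0.3 | ρ = 0.5 | ρ = 0.7 | ρ = 0.8 |
|---|---|---|---|---|---|
| 25% | 9 | 0.5% | 1.5% | 2.8% | 3.7% |
| 50% | 18 | 1.0% | 2.7% | 5.4% | 7.0% |
| 75% | 28 | 1.5% | 4.0% | 7.9% | 10.3% |
| 100% | 37 | 1.8% | 5.1% | 9.9% | 12.9% |

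The extremes are 0.09 × 9/155 = 0.0052 and 0.64 × 37/183 = 0.129. In completers per arm, the gain takes 146 to between 146/(1 − 0.0052) ≈ 147 and 146/(1 − 0.129) ≈ 168.

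**3. Bias.** Simulation in SD units with a true week-24 difference of −0.30 and dropout rising with the week-12 score. The slope, the arm-specific rates and ρ are all assumed. In the first two rows the slope is logistic, 1 per SD. The two-visit likelihood estimate stays at about −0.30 when dropout is 24% vs 12%.

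| Dropout, placebo vs erenumab | ρ | Bias in completers-only difference (SD) |
|---|---|---|
| 10% vs 10% | 0.5, 0.7 | about 0 |
| 15% vs 5%, or 20% vs 10% | 0.5, 0.7 | about +0.04, +0.06 |
| 24% vs 12% | 0.5, 0.6, 0.7, 0.8 | +0.05, +0.06, +0.07, +0.08 |

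The last row comes from mean estimates of −0.253, −0.239, −0.232 and −0.221. With 20% in both arms the bias is again essentially 0. A positive value shrinks the apparent benefit. Reversing the imbalance (5% placebo, 15% erenumab) gives about −0.04 and −0.06, which exaggerates it.

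**The case against.** Much of the case on the other side stands.

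- **The change is declared.** A reader who looks only at Section 10 might infer that the switch was undisclosed. The version history states it. What remains is its absence from the list of protocol departures, the missing reason, and the conflict with 8.3.2.
- **Subjects are not dropped from the trial's analysis.** A reader might infer that anyone missing week 24 is excluded altogether. The efficacy analysis set needs only one dose (SAP 6.2), and a week-12 value still counts at week 12. The loss is confined to the week-24 contrast.
- **Separate models at each visit are an inference.** It is the natural reading of an ANCOVA with no visit term, but the SAP does not say so.
- **Loss may be smaller than 20%.** Protocol 10.1 calls that scenario conservative, and Protocol 8.1 asks subjects who stop the product to continue through week 24.
- **The bias needs unequal dropout.** A reader might take from the 24% vs 12% case that these effects would be understated by about a quarter (0.07/0.30 = 23%). The documents give a single 20% with no difference between arms, so they do not support that as an expected result.
- **ANCOVA is a recognised method**, and a rule for one-visit outcomes is reasonable. The fix also adds a covariance choice: Protocol 10.4.2.2 names none, and SAP 9.5.2 assumes first-order autoregressive where applicable.

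None of this gives a reason to extend ANCOVA to two-visit outcomes.

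**Conclusion.** The point holds as a minor one. For MIDAS, GAD-7, ASC-12 and the sleep scores, the SAP departs from the protocol's model without a stated reason, omits the departure from Section 10 and contradicts its own 8.3.2. The cost is roughly 0.5% to 13% of week-24 variance, given 20% dropout and the assumed ranges for m and ρ. Bias is about 0 with equal dropout. It is about 0.04 to 0.08 SD, in either direction, if dropout follows the week-12 score, differs by 10 to 12 points, and ρ is 0.5 to 0.8.

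These outcomes are exploratory and outside the fixed testing sequence. AHMD, MPFID and HIT-6 keep the mixed model, and MFIQ has six post-baseline double-blind visits, so no confirmatory conclusion or type I error rate is touched. BDI-II follows the same two-visit schedule, but SAP 9.5.3 describes only category and shift summaries for it, so the method for its change score is unclear.

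**What to change.** - **SAP 9.5.3:** limit ANCOVA to outcomes with one post-baseline visit. For two-visit outcomes use the protocol's model (treatment, baseline, stratification factor, visit, treatment by visit) with an unstructured 2×2 covariance, and report both visits. State whether this covers BDI-II change from baseline.
- **Cumulative MIDAS:** take the treatment effect as the sum of the week-12 and week-24 contrasts, with its variance from the same model. This also settles the case where one visit is missing.
- **SAP 8.3.2 and Section 10:** make 8.3.2 agree with 9.5.3, and list any remaining ANCOVA use in Section 10 with its reason. There may be none: PGIC and HRU are the instruments with a single post-baseline double-blind visit, and they are handled by category and by occurrence.

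The cost is a few lines of SAP text and a covariance setting on model code already needed for HIT-6 and MFIQ. No data collection changes, and there is no material loss of efficiency.
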